- Body mass index of $\geq 27.5 \text{ kg/m}^2$ (to ensure we are working with chronic, unresolved low grade inflammation not just the result of injury – those with a BMI of $>25 \text{ kg/m}^2$ have clinically raised levels of CRP compared with those with a BMI of $<25 \text{ kg/m}^2$ [33]).
- Average daily physical activity level (PAL - total energy expenditure/resting energy expenditure) of <2.00 , to ensure the individual is not highly active.
- Have no physical impairment unrelated to the knee that would prevent safe participation and their ability to comfortably complete cycling exercise under sub-maximal conditions.

Inclusion and exclusion criteria

Inclusion	Exclusion
Male or post-menopausal females	Inability to undertake cycling exercise safely**
Clinically diagnosed with knee Osteoarthritis including radiographic confirmation	Use of prescribed anti-inflammatory medication***
Oxford Knee Score ≥ 20 to ≤ 35 for index knee	Current smoker [34] (or having quit <6 months ago)
Aged 45-69 years	Has a diagnosis of diabetes or other metabolic disorder
BMI $\geq 27.5 \text{ kg/m}^2$ to $\leq 40.0 \text{ kg/m}^2$	Use of other medications that might interfere with study outcomes
Daily physical activity level $<2.00^*$	Recent (within last 3 months) change in body mass of $>5\%$

	Currently engaged in an ongoing programme of physiotherapy treatment
	Currently on waiting list or having had surgery for Osteoarthritis on the index knee (prior OA related surgery permitted on other knee if this is greater than 12 months prior to enrolment)
	Having had major hip/knee surgery within preceding 12 months
	Individuals with a blood pressure of greater than 180/110
	Currently pregnant or intending to become pregnant during the study

*Assessed during a preliminary period of ≥ 7 days via accelerometer.

**Assessed during pre-screening via physical activity readiness questionnaire (PAR-Q+).

***Patients that occasionally use NSAIDS will be asked to use paracetamol as a 'rescue medication' if they experience pain during the trial, with a minimum of a 3-day washout period prior to the trial.

Recruitment

Patients will be recruited through Virgin Care acting as a patient identification centre:

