- 1) Potentially eligible patients attending a Health Optimisation clinic for Osteoarthritis (for individuals with a BMI >30 kg/m² or current smokers) as part of services provided by Virgin Care will be provided with study information. These individuals have been previously clinically diagnosed with knee osteoarthritis by a physiotherapist or general practitioner before being referred to the Health Optimisation Clinic. Physiotherapists or exercise instructors delivering these classes will provide study information (Participant Information Sheet) to potentially relevant individuals based upon age, body mass and Oxford Knee Score as described in inclusion criteria above.

As part of this identification process, only the direct care team will interact with the patients to the point at which individuals are provided with study information.

Sample size

A previous intervention conducted in sedentary overweight and obese women using the same energy restriction model for 3 weeks^[7], established an effect size of 1.22 for the change in CRP with dietary energy restriction and vigorous intensity exercise 5 x per week. Using this effect size, an α of 0.05, and a power of 80%, it is estimated that a sample size of 8 would be

required for a two-tailed paired comparison. However, as we would hypothesise that the effect of the diet only intervention would be less, due to the lesser energy restriction and independent impact of exercise training upon CRP, an estimated effect size of 0.85 is proposed. Using an α of 0.05, and a power of 80%, it is estimated that a sample size of 13 would be required for a two-tailed paired t-test. Assuming a dropout rate of ~25%, we would aim to recruit ~16 individuals in each intervention arm. Between-group comparisons will be exploratory in nature, to determine sample sizes of future studies comparing the efficacy of the conditions.

Group allocation/Randomisation

Following screening/baseline measures of those included, participants will be allocated to either intervention group 1 (Diet restriction) or intervention group 2 (Diet restriction + Exercise) by an individual outside of the research team who will have no interaction with participants. To protect against chance imbalance between the two groups, this will be conducted via minimisation accounting for participant sex, age, BMI, and Oxford Knee Score.

Outcome measures

Primary outcome variable

- Change in the primary clinical biomarker of systemic inflammation (CRP).

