All participants (regardless of intervention group) will attend 3 separate trial visits in which the following measurements/tests will be performed.

- DEXA scan + anthropometrics
- Resting metabolic rate (RMR)
- Venous blood sample (for collection of plasma and serum)
- Functional tests
- Self-report measures
- Experimental pain measurements

Wash-in period

Following trial visit 1, participants' will complete a four-week wash-in period (allowing participants to act as their own control). Throughout the wash in period, participants will be asked not to make any substantial changes to their normal lifestyle. Food diaries and activity monitoring will also be completed for 1-week of the wash-in period to enable prescription of the energy restriction diet. At the end of this 4-week period, participants will return for another trial visit to determine the stability of biomarkers and other outcomes under stable lifestyle conditions.

Intervention group 1

For the 4-week intervention period, participants in intervention group 1, will reduce their habitual diet by 5000 kcal per week, prescribed individually based on their 7-day food diary

and physical activity monitoring (i.e., energy intake and energy expenditure). The diet restriction will be based on an absolute energy deficit achieved by the intake of smaller food portions. This will be subtracted from their energy expenditure (Actiheart™) rather than energy intake to avoid issues with participants' under-reporting food intake. We will induce this energy deficit by multiplying the weight of all individual foods from the 7-day diary by a factor gathered from the energy expenditure data, allowing us to determine the desired energy intake for the intervention period.

Intervention group 2

For the 4-week intervention period, as per the diet alone group, participants in intervention group 2 will reduce their habitual diet by 5000 kcal per week. However, there will be the addition of five, 30-minute aerobic exercise sessions per week. Each participant will be provided with a cycle ergometer which will be set up in the participants home, where all exercise training sessions will take place. Due to the progressive nature of the exercise increasing weekly, researchers will check-in with participants weekly via video/telephone call to ensure there are no issues. Participants will also be required to wear a HR monitor for at least 1 exercise session a week for us to determine that the intensity is increasing weekly.

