Exercise sessions will be based upon individuals' perception of intensity using the 6-20 rating of perceived exertion (RPE) scale (where 6 = no exertion and 20 = maximal exertion). The target intensity based upon RPE will progressively increase throughout the duration of the training. During week 1 of intervention, the target intensity will be an RPE of 12 for 30 minutes, RPE of 13 for week 2, RPE of 14 for week 3 and RPE of 15 during week 4. These target intensities span the range from moderate-intensity exercise to the lower boundary of vigorous-intensity exercise.

[figure not shown]

Figure 2. Detailed schematic of the two trial periods.

Procedures

Blood sampling

Blood samples of 20ml will be collected via venepuncture using local procedures, processed by centrifugation immediately (plasma samples) or left to clot for 30 minutes then processed (serum samples). In both cases, samples will be aliquoted into 500 microlitre cryovials and stored in ultralow temperature freezers at -80°C until use. Trial specific Instructions will cover laboratory processing of samples. Measurements of biomarkers will be by established laboratory assays, either immunoassay or electrochemiluminescence (Mesoscale Discovery), previously validated for use with plasma or serum, [name] Laboratory, Oxford; with CRP, glucose, NEFA and total/HDL cholesterol analysed using a clinical chemistry analyser at the Human Physiology laboratories at the University of Bath.

Lifestyle intervention

Diet

Based on their habitual dietary choices, participants' calorie intake will be reduced by 5000kcal.week⁻¹ relative to measured energy expenditure during the week. The dietary restriction will be based on an absolute energy deficit achieved by the intake of smaller food portions.

Exercise

Participants will take part in 5 moderate-vigorous intensity (based upon RPE) stationary cycling exercise sessions per week for 30 minutes. This is in line with weekly recommendations of exercise for adults.

Disadvantages/risk and discomfort

Participants will be asked to give up their time, for pre-screening preliminary testing and 3 laboratory visits at the University of Bath. This might pose an inconvenience for some people.

Venous blood samples will be collected by venepuncture which can cause minor discomfort during the procedure and may result in minor bruising. In rare cases, there is the chance of

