infection, though the occurrence of such events are further minimised by our strict institutional adherence to best practice and standard operating procedures.

Assessment and clearance for submaximal exercise will be determined by Physiotherapists employed by Virgin Care as part of the participant identification process. This will reduce the risk of adverse events during exercise testing. Based on participants' choice, exercise sessions will be subsequently conducted at the laboratories at the University of Bath or at home with equipment provided by the researchers – this option will be subject to the participants confirming that an additional individual will be available to be present during home-based training.

Symptoms in response to the prescribed exercise will be monitored throughout the duration of the intervention. Patients will be asked to rate pain in response to exercise using a 0-10 numerical rating scale. Scores greater than 6 during or after exercise will result in some reduction in intensity of exercise ^[35]. Additionally, should elevated joint pain persist for greater than 24 hours than the pre-exercise level, then the intensity of the subsequent session will be reduced. This will be continued until symptoms subside.

We will measure body composition and visceral adipose tissue in participants on the three trial days using a DEXA scanner. A DEXA scanner is a non-invasive radiographic technique that uses very low radiation (total protocol dose of 0.03 mSv) which is equivalent to experiencing a few days of average natural background radiation in the UK.

In line with current government guidelines and university policy surrounding COVID-19, strict social distancing measures will be in place when possible, and where not possible, suitable PPE will be provided for researchers and participants. If the participant or researcher present with any COVID-19 symptoms during the period of the research project, they will be required to quarantine in line with Government advice. Further, for the collection of expired gas during exercise, Douglas bags will be fitted with filters to prevent the potential spread of COVID-19. All lab spaces/research areas will be thoroughly cleaned and sanitized between each participant visit.

The above will be explained to the potential participant verbally and in the participant information sheet to ensure that they are fully informed before giving consent.

Methods

Blood storage

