- Dynamic mechanical allodynia (ALL) will be measured using a brush as a light tactile stimulator acting as moving innocuous stimuli: exerting ~200-400nM of force. This will be applied with a single length stroke of ~2cm over the skin.

Storage and management of data and confidential information

Blood samples will be partially processed/analysed on trial days under an anonymised participant identification number and then kept locked away in the laboratory, at -80°C, which will only be accessible to the researchers involved. After analysis, samples will be stored until the work has been published. Any published work from the study will include no identifiable participant information. Participant information and results from the study will be stored in an Excel data sheet, located, and maintained on a university computer, locked with a password shared only between the research team.

Rewards and feedback

As part of the intervention period, if allocated to the exercise group, participants will be given a cycle ergometer for use in their own home for the duration of the study period. Individuals in the diet only group will be offered a cycle ergometer for one month and an initial supervised exercise session after the completion of the study.

The two intervention arms are designed to produce health benefits to the participants, including improved aerobic capacity and potentially reduced knee pain and increased knee function as a result of the exercise intervention. Individuals in the diet only group would be expected to lose a small amount of body mass. Individualised feedback documents will be given to all participants, which will highlight improvements that could be made to their daily routines i.e., diet and exercise. This document will also include information gathered from all tests i.e., body composition, fitness level and blood tests.

References

1. Cross, M., et al., *The global burden of hip and knee osteoarthritis: estimates from the global burden of disease 2010 study*. *Annals of the rheumatic diseases*, 2014. **73**(7): p. 1323-1330.
2. Berenbaum, F., *Osteoarthritis as an inflammatory disease (osteoarthritis is not osteoarthrosis!)*. *Osteoarthritis and cartilage*, 2013. **21**(1): p. 16-21.
3. Bauer, D., et al., *Classification of osteoarthritis biomarkers: a proposed approach*. *Osteoarthritis and Cartilage*, 2006. **14**(8): p. 723-727.

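### The protocol places all exercise training at home without condition in one section, but in another offers laboratory or home and makes home training depend on a companion

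*Protocol*

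**What the plan says.** Two sections of the protocol state where the exercise sessions are held.

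- **Study design, Intervention group 2.** Each participant is given a cycle ergometer "which will be set up in the participants home, where all exercise training sessions will take place". Researchers check in weekly by video or telephone, and a heart-rate monitor is worn for at least one session a week. No other site is mentioned and no condition is attached.
- **Disadvantages/risk and discomfort.** According to the participant's choice, "exercise sessions will be subsequently conducted at the laboratories at the University of Bath or at home with equipment provided by the researchers". The sentence continues: "this option will be subject to the participants confirming that an additional individual will be available to be present during home-based training".

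Three other places touch on the matter without settling it.

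- **Lifestyle intervention, Exercise** prescribes five moderate-to-vigorous "stationary cycling exercise sessions per week for 30 minutes" and names no place.
- **Disadvantages/risk and discomfort**, opening sentence, describes the time commitment: "Participants will be asked to give up their time, for pre-screening preliminary testing and 3 laboratory visits at the University of Bath".
- **Rewards and feedback** says that in the exercise group "participants will be given a cycle ergometer for use in their own home for the duration of the study period".

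**The concern.** The intervention section fixes one site for every session. The risk section offers two sites and restricts one of them. Staff who set up training from the intervention section would have a participant without a companion exercise at home, which the risk section does not allow. A participant who relies on the risk section and asks to train in the laboratory has no such option in the intervention section.

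The companion requirement is a safety condition on exercise whose target rises from RPE 12 in week 1 to RPE 15 in week 4. It appears only in the risk section, not where the intervention is specified. What participants are told before consent about site, companion and attendance also depends on which text is used. So does any later description of how the exercise was delivered.

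**Working it through.** No published figure has to be reproduced. The check is a comparison of texts, followed by a simple bound on its reach.

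**1. Do the two sections describe the same sessions?** Yes. The risk section does mention submaximal exercise just before, in connection with physiotherapist clearance. However, the sentence at issue refers to exercise sessions in the plural that follow that clearance, to equipment supplied by the researchers, and to home-based training. Those are the training sessions of Intervention group 2, not the single submaximal test under Preliminary testing. The wording of the companion condition is a little loose as to which option it qualifies, but its closing words tie it to training at home.

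**2. For whom can both be followed?**

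| Exercise-arm participant | Intervention group 2 | Disadvantages/risk and discomfort | Compatible? |
|---|---|---|---|
| Chooses home, companion available | Home | Home allowed | Yes |
| Chooses home, no companion | Home | Home not allowed | No |
| Chooses laboratory, with or without a companion | Home | Laboratory | No |

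**3. Can the incompatible cases arise?** Yes. The Participants section requires that candidates "Have no physical impairment unrelated to the knee that would prevent safe participation and their ability to comfortably complete cycling exercise under sub-maximal conditions". The exclusion table adds inability to cycle safely, assessed by PAR-Q+. Both concern the person's fitness to exercise, and no listed criterion requires a companion. Allocation is by minimisation on sex, age, BMI and Oxford Knee Score, so availability of a companion plays no part in it either.

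**4. Does any other text decide between them?** None that can be seen. The Exercise procedure gives frequency, intensity and duration only. The home ergometer under Rewards and feedback and the three laboratory visits in the time commitment fit home-only training more easily, but neither excludes laboratory training. The three visits match the trial visits that all participants attend in either arm. Figure 2 and the participant information sheet are not available here, so whether they state the setting is unknown.

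**5. Reach.** The Sample size section says "we would aim to recruit ~16 individuals in each intervention arm".

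- Participants in conflict: from 0 to about 16, depending on preferences and companions, on which the protocol gives no information.
- Sessions per exercise-arm participant: 5 per week × 4 weeks = 20.
- Cycling time if all were in the laboratory: 20 × 30 min = 600 min = 10 hours, travel aside. If none were, 0.
- Laboratory training sessions across the arm: from 0 to about 16 × 20 = 320. The upper end assumes that nobody drops out and that everyone trains wholly in the laboratory.

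These are outer limits, not estimates.

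**The case against.** The strongest reply is that the risk section largely takes care of the problem. It gives a participant without a companion somewhere to train, and it ends by saying that its contents will be explained to candidates verbally and in the information sheet before consent. Harm would require staff to follow one section and ignore the other. That lowers the practical risk, but it does not remove the contradiction: the intervention section still says that all sessions are at home, and the companion condition is absent from it.

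It can also be said that the supporting points are weak.

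- The time-commitment sentence and the laboratory option stand in the same section, so a reader of the whole section does learn that laboratory training is possible. This is fair. The time statement is incomplete for someone who trains in the laboratory, but it is not a second contradiction.
- The home ergometer does not exclude laboratory training. This is also fair, and it is only a matter of alignment.
- A range from 0 to about 320 sessions says little. Agreed: it shows only that the protocol does not allow the extent to be pinned down.

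Finally, frequency, duration and RPE targets are stated without reference to site, so the prescribed exercise dose does not depend on which rule holds. That is right, and it limits the seriousness of the point without answering it.

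**Conclusion.** The point holds. The two sections cannot both be followed for an exercise-arm participant who chooses the laboratory or has no companion, and nothing visible in the protocol says which governs. The text applies to the exercise arm only, about 16 people as planned, and the number in actual conflict lies between 0 and about 16.

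The consequences are for consistent delivery of the exercise and for a safety condition. The definition of the CRP endpoint, the sample size and the paired within-arm comparison are unaffected. The conclusion rests on the visible text and assumes that the figure and the information sheet, which were not available, do not themselves settle the setting. Even if they did, the two sections would still need to agree. This should be corrected, but it does not threaten the primary analysis.

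**What to change.** Reconcile Intervention group 2 with Disadvantages/risk and discomfort so that both state the same rule on where sessions are held, together with whatever safety condition belongs to it. Then bring the time-commitment sentence, the ergometer text under Rewards and feedback, and the participant information sheet into line. Which rule on setting and companionship applies is for the clinical team to decide.

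The cost is protocol wording and a check of the information sheet. No design parameter or analysis changes.
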